8.3.2. Secondary Efficacy Analyses

The secondary efficacy endpoints are listed in [Table 1](#) and will be analyzed as described below.

8.3.2.1. Change from Baseline to Week 16 Endpoints

8.3.2.1.1. Lund-Mackay and UPSIT Scores

Lund-Mackay scores are based on the centralized imaging data assessments and scored by blinded central reading at the imaging core laboratory. The Lund-Mackay system is based on localization with points given for degree of opacification: 0 = normal, 1 = partial opacification, 2 = total opacification. These points are then applied to each sinus (maxillary, anterior ethmoid, posterior ethmoid, sphenoid, and frontal sinus) on each side. The osteomeatal complex on each side is graded as 0 = not occluded, or 2 = occluded, deriving a maximum score of 12 per side, for a total score ranging from 0 to 24 ([Lund, 1993](#)). Of note, an aplastic (absent) frontal sinus receives a score of 0.

The UPSIT test consists of four booklets, each containing 10 odorants with one odorant per page ([Doty, 1984](#)). The test-time is about 15 minutes. The stimuli are embedded in 10–50 μm diameter plastic microcapsules on brown strips at the bottom of each page. Above each odorant strip is a multiple-choice question with four alternative words to describe the odor. The subject is asked to release the odorant by rubbing the brown-strip with the tip of a pencil and to indicate which of four words best describes the odor. An UPSIT score will only be derived if all 40 responses are non-missing. A higher UPSIT score indicates better olfaction. Anosmia categories for the UPSIT score are defined as:

- Anosmia = 0 - 18
- Severe Microsmia = 19 – 25
- Moderate Microsmia = 26 - 30
- Mild Microsmia = 31 – 34

- Normal = 35 – 40

For the change from baseline to Week 16 in Lund-Mackay and UPSIT scores, the primary analysis will be ANCOVA without MI if the number of subjects overall with a missing change from baseline value to Week 16 is < 10% for the respective endpoint. If the number of subjects overall with a missing change from baseline value to Week 16 is $\geq 10\%$ for the respective endpoint, the primary analysis will be ANCOVA with MI, with an MI procedure similar to that described in [Section 8.3.1.2](#), and ANCOVA without MI will be performed as a sensitivity analysis. For the Lund-Mackay and UPSIT score multiple imputation, step 1 for imputing intermittent missing values will be skipped since Lund-Mackay and UPSIT scores can only be monotone missing, as they are only collected at Weeks 0 and 16. The ANCOVA models will be analogous to those described in [Sections 8.3.1.3](#) and [8.3.1.4](#), with the baseline score specific to each endpoint included as a covariate.

Bar graphs of the LS mean change from baseline to Week 16 by treatment group, including 95% CIs, for Lund-Mackay and UPSIT scores will be provided, using the primary analysis approach for each endpoint based on the amount of missing data as described in [Table 1](#).

The number and proportion of subjects in each anosmia category will be summarized by visit, including baseline, using as observed data.

CT scan and UPSIT data will also be presented in by-subject data listings.

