2.5. Sample Size Determination

A total sample size of approximately 100 subjects (approximately 50 per treatment group, randomized in a 1:1 ratio) is estimated to provide approximately 90% power to detect a treatment difference of 12.0 between GB001 and placebo at a 0.050 two-sided level of significance for the primary endpoint of change from baseline to Week 16 in SNOT-22 score, assuming a common standard deviation (SD) of 16.8 and a dropout rate of 15% using a two-sided t-test.

A total sample size of approximately 64 subjects in the CRSwNP stratum (approximately 32 per treatment group, randomized in a 1:1 ratio) is estimated to provide approximately 80% power to detect a treatment difference of 1.3 between GB001 and placebo at a 0.050 two-sided level of significance for the secondary endpoint of change from baseline to Week 16 in NPS, assuming a common SD of 1.7 and a dropout rate of 15% using a two-sided t-test.

Therefore, the total sample size of approximately 100 subjects overall will consist of approximately 64 subjects in the CRSwNP stratum and 36 subjects in the CRSsNP stratum.

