3. GENERAL ANALYSIS AND REPORTING CONVENTIONS

All analyses will be performed using SAS® System (SAS Institute Inc., Cary, NC) version 9.4 or later.

Categorical variables will be summarized using counts (n) and percentages (%) and will be presented in the format “n (xx.x)”. If a count is 0, no percentage will be shown. To ensure completeness, summaries for categorical and discrete variables may include all categories, even if no subjects had a value in a particular category. Additionally, for missing data, a category of “Missing” will be presented as needed.

Continuous variables, unless otherwise stated, will be summarized using descriptive statistics: number of subjects with non-missing data (n), mean, standard deviation (SD), median, 25th and 75th percentiles, minimum, and maximum. Descriptive statistics on select measures may also include the standard error (SE) and 95% confidence interval (CI) for the mean. In general, rounding rules for reporting continuous descriptive summary statistics are as follows:

- If the original values have 0 or 1 decimal places: mean, median, 25th and 75th percentiles will be reported to one more decimal place than the original values, and SD and SE will be reported to 2 more decimal places than the original values
- If the original values have 2 or more decimal places: mean, median, 25th and 75th percentiles, SD, and SE will all be reported to 3 decimal places

Minimum and maximum will always be reported to the same decimal places as the original values, up to a maximum of 3 decimal places. Percent change from baseline will be reported to 1 more decimal place than change from baseline, up to a maximum of 3 decimal places.

Efficacy results will be summarized by various measures including but not limited to least squares (LS) means, differences in LS means, SEs, odds ratios (ORs), hazard ratios, rate ratios, p-values, and two-sided 95% CIs. The SEs, LS means, differences in LS means and corresponding CIs will be reported per the rules above, with the CIs following the same rounding rules as the mean, ORs, hazard ratios, rate ratios, and corresponding CIs will be reported to 3 decimal places, and percentage reductions and corresponding CIs will be reported to 1 decimal place. P-values will be reported to 4 decimal places, with values less than 0.0001 displayed as < 0.0001 and values greater than 0.9999 displayed as > 0.9999. All statistical hypothesis testing will be at an 0.050 two-sided level of significance.

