8.3.1.2. MMRM with MI

Missing SNOT-22 total scores at post-baseline visits will be imputed using an MI approach. Missing SNOT-22 total scores at baseline will not be imputed.

The following steps will be performed:

- Step 1: Intermittent missing values will be imputed using the Markov Chain Monte Carlo (MCMC) method ([Schafer, 1997](#)), using a noninformative prior (Jeffreys) for the prior information for the means and covariances and expectation-maximization (EM) for the initial mean and covariance estimates.
- Step 2: Monotone missing values will then be imputed using a linear regression model ([Allison, 2005](#)) including the imputed intermittent missing values in step 1. A monotone missing pattern is such that in the event that a variable is missing it is implied that all subsequent variables are also missing (e.g., once a subject withdraws from study, no additional data is expected for that subject).
- For each step, MI will be performed within each treatment group with covariates for disease status stratification factor values used for randomization (CRSwNP with

comorbid asthma, CRSwNP without comorbid asthma, and CRSsNP), region (United States, Eastern Europe), and non-missing values for baseline SNOT-22 total score and Weeks 4, 8, 12, and 16 SNOT-22 total scores. Should convergence issues occur due to small cell size for the categorical covariates at either step, the categorical variable(s) causing convergence issues will be removed from the model.

- Missing change from baseline and percent change from baseline in SNOT-22 total scores will be computed from the imputed SNOT-22 total scores.
- The analysis of the primary endpoint as described in [Section 8.3.1](#) will be performed for each complete, imputed dataset.
- For step 1, fifty imputations will be performed. For step 2, 1 imputation will be performed if 50 imputations were performed for step 1. Fifty imputations will be performed for step 2 if step 1 was skipped (e.g., for assessments only collected once post-baseline or for endpoints without intermittent missing values).
- Results of the MMRM on the multiple imputed data sets will be combined to generate an overall estimate and associated variance using Rubin's rules ([Rubin, 1987](#)).

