8.3.1.3. ANCOVA without MI

For ANCOVA without MI, the models will include covariates for treatment group, disease status stratification factor values used for randomization (CRSwNP with comorbid asthma, CRSwNP without comorbid asthma, and CRSsNP), region (United States, Eastern Europe), and baseline SNOT-22 total score.

Descriptive statistics for change from baseline to Week 16 along with the LS means, SEs, and corresponding 95% CIs for each treatment group will be provided. The difference in LS means, SE, corresponding 95% CI, and p-value for the GB001 40 mg group versus placebo will also be constructed from the ANCOVA model. Results will be presented for the total score only.

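### The multiple imputation planned as primary for Lund-Mackay and UPSIT uses no post-baseline information, so it nearly repeats observed-case ANCOVA and does not address dropout related to on-study symptom course

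*SAP*

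**What the plan says.** SAP 8.3.2.1.1 and Table 1 choose the analysis of Lund-Mackay and UPSIT by the fraction of subjects without a Week 16 change. Below 10%, ANCOVA without imputation is primary. At 10% or more, "the primary analysis will be ANCOVA with MI, with an MI procedure similar to that described in" Section 8.3.1.2, and ANCOVA without imputation becomes the sensitivity analysis. The intermittent-missing step is dropped because the SAP treats both scores as collected only at Weeks 0 and 16.

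The borrowed procedure is this: "For each step, MI will be performed within each treatment group with covariates for disease status stratification factor values used for randomization", plus region and the score's own baseline and visit values. The ANCOVA is given in SAP 8.3.1.3: "the models will include covariates for treatment group, disease status stratification factor values used for randomization", region and baseline score, all as main effects. Section 8.3.2.1.1 substitutes each endpoint's own baseline. It names no other imputation variable.

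**The concern.** For SNOT-22 the template carries Weeks 4, 8 and 12 into the imputation of Week 16. For Lund-Mackay and UPSIT nothing comparable remains. What a leaver reported before going (SNOT-22 visits, daily smell scores) is not used. If subjects leave because they are doing badly, the imputed values follow the pattern of similar subjects at baseline, not of subjects on a similar course. The primary and sensitivity analyses then rest on the same information, and their agreement could be read as robustness to missing data when that question has not been tested.

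**Working it through.** **1. The plan's own figures.** The primary sample size uses n = 50 × 0.85 = 42.5 per arm, "assuming a common standard deviation (SD) of 16.8 and a dropout rate of 15% using a two-sided t-test", and a difference of 12.0 (SAP 2.5). Noncentrality = 12.0 / (16.8 × √(2/42.5)) = 3.29, giving power 0.902 against the stated 90%. For NPS, n = 32 × 0.85 = 27.2 and 1.3 / (1.7 × √(2/27.2)) = 2.82, giving 0.790 against 80%. Both reproduce. Neither document states power, effect size or SD for Lund-Mackay or UPSIT.

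**2. How likely the imputation branch is.** With 100 subjects, P(at least 10 missing) is 0.945 at 15% missing, 0.549 at 10% and 0.028 at 5%. The first figure applies only if every dropout lacks a Week 16 value.

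**3. Why imputation adds little.** Let X be the ANCOVA design matrix, split into observed (o) and missing (m) rows, and let b be the observed-case estimate. If missing values are drawn as X_m b* + e*, with b* centred on b and e* on zero, the completed-data estimate has expectation

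(X_o'X_o + X_m'X_m)⁻¹ (X_o'X_o b + X_m'X_m b) = b.

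Imputation from the ANCOVA's own covariates, pooled over arms, therefore returns the observed-case estimate apart from simulation noise. The SAP imputes within arm, which adds treatment-by-strata, treatment-by-region and treatment-by-baseline terms and an arm-specific residual variance. Its result can differ from b, but only as far as the arm-specific coefficients differ.

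**4. Simulation.** 50 per arm, three strata, two regions, about 15% missing, 50 imputations, Rubin's rules and 500 trials per setting. The effect (0.70 residual SD), correlations and dropout mechanisms are assumptions.

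- Missing completely at random: by-arm imputation and observed-case ANCOVA correlate 0.994, with RMS difference 0.024 SD.
- Dropout depending on baseline, common slope: 0.977 and 0.051 SD. Mean SE is 0.2295 against 0.2193 (ratio 1.05). In the on-study settings below the ratio is about 1.02 (for example 0.2228 / 0.2180).

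Placebo dropout driven by poor on-study SNOT-22 course; bias against full-data ANCOVA in residual SD, positive meaning toward zero (Monte Carlo SE about 0.004):

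| Assumed correlation | Observed-case ANCOVA | Planned by-arm MI | By-arm MI plus on-study SNOT-22 |
|---|---|---|---|
| 0.2 | 0.032 | 0.031 | -0.005 |
| 0.5 | 0.084 | 0.087 | 0.001 |
| 0.8 | 0.136 | 0.137 | -0.002 |

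Dropout depending on baseline, with baseline slopes that differ between arms:

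| Slope difference | Observed-case ANCOVA | Planned by-arm MI |
|---|---|---|
| 0 | 0.004 | 0.002 |
| -0.2 | 0.036 | -0.001 |
| -0.4 | 0.068 | 0.000 |

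**5. Sensitivity to the dropout mechanism.** With effect 0.5 SD, about 14% dropout, 2,000 runs per setting and correlations from 0.3 to 0.7, the bias toward the null is 0.05 to 0.11 SD when only placebo dropout is symptom-driven. It is 0.02 to 0.05 SD when the same rule applies in both arms. Runs with 11-14% missing that include leavers with only early SNOT-22 values give 0.04-0.08 and 0.01-0.025 SD. In those runs, SNOT-22 imputed first and then used as an auxiliary brings the bias to within 0.005 SD, at an SE 0-2% larger.

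**The case against.** Four stronger readings are tempting, and the documents do not support them.

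- *The imputation reproduces observed-case ANCOVA exactly and cannot reduce dropout bias.* The variable list is the same, but fitting within arm makes the imputation model richer. The second table shows it removing bias when dropout depends on an effect-modifying baseline.
- *The comparison is with completers only.* The Schedule of Activities lists UPSIT at the early-withdrawal and early-discontinuation visits, and CT there if after Visit 5. SAP 3.1 uses windows without gaps that open just after the first dose. For an endpoint with one post-baseline visit, such values would on a natural reading fall in Week 16.
- *The planned 15% dropout means imputation will be primary.* For the same reason, 15% dropout need not be 15% missing. If half of a 14% dropout supplied such a value (an assumption), 7% would be missing, imputation would not be expected to trigger, and the bias would roughly halve.
- *The bias could create a false benefit.* In the on-study dropout scenarios run it is toward the null. Even 0.11 SD is about half the estimate's own SD of about 0.22.

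It is also fair that these are two of several secondary endpoints in a Phase 2a study whose stated hypotheses concern SNOT-22 and NPS (Protocol 9.1). The wording in 8.3.2.1.1 asks only for a similar procedure, so it does not literally forbid auxiliary variables. But where the SAP adds an imputation variable it says so: 8.3.2.1.2 names Week 20 values for NC and TSS.

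What survives is narrower: no post-baseline variable is specified. Relevant data may exist even at Week 16. UPSIT is not scored if any of its 40 responses is missing, and Protocol Appendix 11 allows SNOT-22 at home but lists no home alternative for CT.

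**Conclusion.** The point holds in limited form. As written, the imputation nearly repeats observed-case ANCOVA and leaves bias from dropout related to on-study course unchanged, so agreement with the named sensitivity analysis is not evidence on that question. The remaining bias is about 0.01-0.05 SD with one dropout rule in both arms and about 0.04-0.11 SD if only placebo dropout is symptom-driven. It is toward the null in these scenarios, and smaller if early-withdrawal values are windowed into Week 16.

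These sizes rest on assumed correlations of 0.3-0.7 and assumed mechanisms; the documents give neither. With a correlation near zero, both the bias and the gain from an auxiliary disappear. The structural finding, that no post-baseline information enters, rests on the SAP text and not on the simulation. It is worth correcting because the SAP already uses on-study history for its primary endpoint and the correction is cheap.

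**What to change.** In SAP 8.3.2.1.1, add on-study SNOT-22 to the by-arm imputation model for both endpoints:

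1. Impute missing SNOT-22 visits by the 8.3.1.2 steps, run for this purpose whatever the SNOT-22 missing fraction. Otherwise those data sets are planned only when SNOT-22 itself reaches 10% missing.
2. In each completed data set, impute Lund-Mackay and UPSIT from strata, region, own baseline and one SNOT-22 summary, such as the Week 16 score. The AM loss-of-smell score is optional for UPSIT.
3. Do not add Week 8 NPS to the pooled model; by design it does not exist in CRSsNP.
4. Keep the ANCOVA and the analysis without imputation unchanged.

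Cost: one or two more parameters per arm, an SE about 0-2% larger, and slightly more programming on data already collected. The result still assumes data missing at random given the auxiliary. The change should be fixed before unblinding; later it would have to be reported as post hoc under SAP Section 1.

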8.3.2.1.2. NPS and Symptom Scores

The bilateral endoscopic NPS is the sum of the right and left nostril scores, as evaluated by means of blinded, centrally read nasal endoscopy and ranges from 0-8. NP is graded based on polyp size: 0 = No polyps, 1 = Small polyps in the middle meatus not reaching below the inferior border of the middle turbinate, 2 = Polyps reaching below the lower border of the middle turbinate, 3 = Large polyps reaching the lower border of the inferior turbinate or polyps medial to the middle turbinate, and 4 = Large polyps causing complete obstruction of the inferior nasal cavity.

On a daily basis, from Visit 1 and throughout the study, the subject will use a Diary to: Respond to the AM and PM individual rhinosinusitis symptom questions using a 0–3 categorical scale (where 0 = no symptoms, 1 = mild symptoms, 2 = moderate symptoms and 3 = severe symptoms) for the following symptoms:

- congestion and/or obstruction (i.e. NC score)
- anterior rhinorrhea (runny nose)
- posterior rhinorrhea (post-nasal drip)
- loss of sense of smell

The above symptom scores will be recorded directly in the daily Diary. For post-baseline visits, the average of the daily symptom scores over the prior 4 weeks will be used to determine the value for that visit, if at least 50% of the scores were completed over the prior 4 weeks, and will

be calculated separately for AM and PM scores. The TSS is the sum of the scores from the 4 symptom categories (congestion and/or obstruction, anterior rhinorrhea, posterior rhinorrhea, loss of sense of smell), ranges from 0–12, and will be calculated separately for AM and PM scores.

For the change from baseline to Week 16 in NPS, AM NC score, and AM TSS, the primary analysis approach will depend on the amount of missing data for each endpoint, based on the same criteria for the primary endpoint as described in [Section 8.3.1](#). The MMRM models will be similar to those described in [Sections 8.3.1.1](#) and [8.3.1.2](#), with the baseline score specific to each endpoint included as a covariate. For NC and TSS MI, Week 20 (Follow-up) values will be included as a covariate in the multiple imputation. For monotone regression, MI is performed sequentially, meaning only the data from weeks prior to the study week with missing data will inform the MI. Therefore, values at Week 20 (Follow-up) will not inform prior weeks. If the analyses fail to converge due to the complexity of model specification, the approaches described in [Section 8.3.1.1](#) will be implemented. The ANCOVA models will be analogous to those described in [Sections 8.3.1.3](#) and [8.3.1.4](#), with the baseline score specific to each endpoint included as a covariate. For the NPS endpoint, the analysis will be conducted within the randomized CRSwNP stratum.

For the change from baseline to Week 16 and change from baseline to all visits through Week 16 in PM NC score, PM TSS, AM and PM anterior rhinorrhea, AM and PM posterior rhinorrhea, and AM and PM loss of sense of smell, the MMRM without MI models described in [Section 8.3.1.1](#) will be used with the baseline score specific to each endpoint included as a covariate.

Actual, change from baseline, and percent change from baseline values in NPS, AM NC score, and AM TSS will be descriptively summarized by visit using MI data if MI is performed. Actual, change, and percent change from baseline values in NPS, NC scores, anterior rhinorrhea scores, posterior rhinorrhea scores, loss of sense of smell scores, and TSS for AM and PM will be descriptively summarized by visit using as observed data.

Bar graphs of the LS mean change from baseline to Week 16 by treatment group, including 95% CIs, for NPS, AM and PM NC scores, AM and PM anterior rhinorrhea, AM and PM posterior rhinorrhea, AM and PM loss of sense of smell, and AM and PM TSS at Week 16 will be provided. Figures of LS mean change from baseline, including 95% CIs, by visit for each of these endpoints will also be provided. The figures will use the primary analysis approach for each endpoint based on the amount of missing data as described in [Table 1](#).

Nasal endoscopy and diary data will also be presented in by-subject data listings.

8.3.2.2. Time to Event Endpoints

Time to first response in NPS is defined as the time from the date of the first dose of study treatment to the first date with ≥ 1 point improvement in NPS from baseline for subjects in the randomized CRSwNP stratum. Subjects in the randomized CRSwNP stratum who do not experience ≥ 1 point improvement in NPS from baseline will be censored at their last post-baseline NPS assessment, or on Day 1 if no baseline NPS assessment or no post-baseline NPS assessment was performed.

CRS exacerbation is defined as deterioration of CRS symptoms requiring treatment with an antibiotic, an anti-inflammatory drug, or a symptom reliever; an Emergency Department visit; or hospitalization (Kuiper, 2018). Time to first CRS exacerbation is defined as the time from the date of the first dose of study treatment to the first date of treatment with an antibiotic, an anti-inflammatory drug, or a symptom reliever, the date of Emergency Department visit, or the date of hospitalization, whichever occurs first. Subjects without a CRS exacerbation will be censored at their last post-baseline CRS exacerbation assessment, or on Day 1 if no post-baseline CRS exacerbation assessment was performed.

For the primary analysis of both time to event endpoints, all data through Week 16 will be included; a sensitivity analysis of both time to event endpoints will be performed including all data.

The number and proportion of subjects with a response in NPS will be summarized for subjects in the randomized CRSwNP stratum. Time to first response in NPS will be compared between treatment groups using a Cox proportional hazards model and will include covariates for treatment group, disease status stratification factor values used for randomization (CRSwNP with comorbid asthma, CRSwNP without comorbid asthma, and CRSsNP), region (United States, Eastern Europe), and baseline NPS.

The number and proportion of subjects with CRS exacerbations will be summarized. Time to first CRS exacerbation will be analyzed using a Cox proportional hazards model and will include covariates for treatment group, disease status stratification factor values used for randomization (CRSwNP with comorbid asthma, CRSwNP without comorbid asthma, and CRSsNP), and region (United States, Eastern Europe).

The exact method will be used to handle ties in event times.

For both time to event endpoints, estimates of the hazard ratio for the GB001 40 mg group versus placebo, corresponding 95% CIs, and p-values will be provided from the model. Percentage reductions and corresponding 95% CIs will also be provided. Kaplan-Meier summaries of the proportion of subjects with response in NPS and separately for the proportion of subjects with a CRS exacerbation over time will also be presented and displayed graphically. The median event time (and other quartiles), if estimable, and corresponding 95% CI based on the Brookmeyer and Crowley method (Brookmeyer, 1982) using the log-log transformation (Kalbfleisch, 1980) will be provided for each treatment group and endpoint.

An additional analysis of the proportion of subjects with a reduction from baseline of ≥ 1 in NPS at Weeks 8 and 16 in the randomized CRSwNP stratum will be analyzed using a logistic regression model to compare the GB001 40 mg group with placebo, using the approach described in [Section 8.3.1.5](#) with NPS score at baseline included as a covariate.

Time to event data will also be presented in by-subject data listings.

